## **7 7. PARAMETERS OF ANALYSIS**

### **7.1 Data Collection and Storage**

Data collection will be triggered by the pneumonia BPA and will be acquired directly from the EHR and stored securely for later analysis. Prior to study initiation, support analysts will conduct detailed requirement explorations to identify necessary data elements and associated data flows, validate accuracy, and evaluate for missing data. Data to be collected includes decision support usage statistics, visit details (e.g., admission and discharge date and time, site of care, ED revisits or hospital readmissions), patient demographics (e.g., age, sex, race, insurance), medication orders and prescriptions (dose, frequency, route, and duration), laboratory testing and results, radiologic studies, and data elements from the decision support applications. Manual review of the EHR will also be conducted where necessary. All data will be stored in REDCap.

### **7.2 Analytic Issues**

There are two sites participating in the study and analysis of the primary objective will be stratified by site to account for site variation. There will be one primary objective per aim evaluated at the alpha 0.05 level. There will be no adjustments to the alpha level for all secondary and exploratory analyses.

## **8 ANALYSIS POPULATIONS**

### **8.1 Intent-to-Treat (ITT) Population:**

The ITT Population includes any participant that is enrolled, randomized into the study. The ITT Population is the primary population for analysis unless otherwise stated.

## **9 BASELINE DATA AND FLOW CHART**

### **9.1 Presentation of Baseline Data**

The following baseline data will be presented by site, season, and intervention group: age, gender, ethnicity, race, comorbidities, clinical presentation, laboratory findings, and radiographic features.

### **9.2 Flow Chart**

The number of enrolled participants will be presented in a flow chart by site and intervention group.

## **10 ANALYSIS OF STUDY OBJECTIVES FOR PHASE 1**

Descriptive analyses will be summarized for continuous variables with mean, standard deviation, median, and interquartile range. Categorical variables will be summarized with frequencies and percentages. Explanatory figures will be generated to evaluate the data distribution. Comparisons of demographic characteristics between intervention groups will be conducted using Pearson Chi-square and Wilcoxon tests appropriately.

All analyses will be performed using R 3.5.0 (r-project.org), SAS version 9.4, or STATA version 15, or updated software from these programs.

### **10.1 Primary Objective**

The primary objective (PO 1) of the study is to compare proportions of participants exclusively receiving guideline-concordant 1st line antibiotic therapy during the first 24 hours of care with or without EHR-based decision support in children 0.6-17 years of age presenting for emergency care. The hypothesis for this primary objective is that the proportion of participants exclusively receiving guideline-concordant 1st line antibiotic therapy during the first 24 hours of care is higher in the group receiving EHR-based decision support vs. the group receiving usual care. This information is captured through chart review and entered in the REDCap database. The antibiotics received by a participant is concordant yes (1) or no (0) based on Appendix 1 table, for this analysis.

The proportions will be compared between the intervention arm versus the control arm using a Cochran-Mantel-Haenszel method in a stratified analysis by site to control for two sites at the alpha 0.05 level. The proportion difference and corresponding 95% confidence interval for concordance of antibiotics with or without adjusting for sites will also be calculated.

We will use a hierarchical and mixed effects logistic regression model, a complex analytic approach which offers flexibility regarding model assumptions and incorporation of cluster-level and individual-level covariates. The outcome is proportions of participants exclusively receiving guideline-concordant 1st line antibiotic therapy during the first 24 hours of care and the main exposure variable is intervention vs. usual care. The month of each participant enrolled will be treated as a random effect. We will also use a weighted, cluster-level logistic regression to compare guideline-concordant antibiotic prescribing between groups. In this analysis, data for each cluster are collapsed into a single summary measure, and the summary measures are then analyzed as if they were raw data, facilitating simple data reporting and interpretation. Important baseline covariates (e.g., age, sex, race, site, season, frequency of bacteremia and other pneumonia-related complications) will also be assessed and included as model covariates.

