1.0 Background

Pneumonia is the most common serious infection in childhood. In the United States (US), pneumonia accounts for 1-4% of all emergency department (ED) visits in children (3-28 per 1,000 US children per year)¹ and ranks among the top 3 reasons for pediatric hospitalization with >100,000 hospitalizations per year (15-22 per 100,000 US children per year)²⁻⁵. Pneumonia also accounts for more days of antibiotic use in US children’s hospitals than any other condition.⁶

Safely reducing inappropriate antibiotic use is critical to slow the progression of antimicrobial resistance, and childhood pneumonia is a key area where substantial improvements can be made. In the 2011 Pediatric Infectious Diseases Society/Infectious Diseases Society of America (PIDS/IDSA) pneumonia guideline, appropriate use of antibiotics was an important area of emphasis.⁷ For presumed bacterial pneumonia, recommendations emphasize the use of a single, narrow-spectrum antibiotic (i.e. amoxicillin or ampicillin). In children <6 years of age treated in the outpatient setting, the guideline recommended considering withholding antibiotics, recognizing that pneumonia in this population is most often caused by viruses. Both of these recommendations were graded as strong and supported by high-quality evidence.⁸⁻¹⁰ Nonetheless, in a large database study we conducted just prior to release of the 2011 guideline, use of broad-spectrum antibiotics was very common among children hospitalized with pneumonia, with substantial differences in antibiotic selection patterns among the various hospitals.¹¹ In that study, use of narrow-spectrum ampicillin was rare (<5%). High rates of broad-spectrum antibiotic use were also noted in a study of children with pneumonia treated and released from US EDs, with <30% of children receiving narrow-spectrum therapy.¹²

Emergency care for childhood pneumonia, including hospitalization rates, varies widely across the nation. A study examining hospital admission rates at 35 US children’s hospitals from 2009-12 showed marked differences in severity-adjusted pneumonia hospital admission rates (median 31%; range 19-69%)¹³. Extending these findings, Florin et al. detected great hospital-level variation in the use of diagnostic tests for children presenting to the ED with pneumonia.¹⁴ They reported that high test-utilizing hospitals had a

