7.0 Study Procedures

7.1 EHR-based Antibiotic Decision Support (P1)

For enrolled subjects assigned to the decision support arm, providers will receive antibiotic recommendations in accordance with the 2011 PIDS/IDSA guideline, tailored to site of care and illness severity. For instance, in young children with mild illness being discharged from the ED, the support tool will offer guidance regarding when a strategy of watchful waiting might be favored over empiric amoxicillin (e.g., fully immunized toddler with upper respiratory tract symptoms). Similarly, in those being admitted to a general ward, the tool will advise consideration of oral therapy in children with good oral intake, or when to consider adjunctive therapy with a macrolide or anti-staphylococcal antibiotic. *Importantly, the tool will offer treatment recommendations only and will not proscribe a specific treatment plan.* If a provider chooses to prescribe therapy not in accordance with the national guideline, the tool will query providers regarding reasons for discrepant prescribing for later analysis.

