7.2 Outcomes (P1)

The primary outcome is the proportion of children exclusively receiving guideline-concordant 1st line antibiotic therapy during the first 24 hours of care (Table 1). For patients discharged from the ED, this will include antibiotics received in the ED as well as antibiotic

Table 1. Concordant Use Definitions for 1st Line Antibiotics¹

Disposition	<6 Years of Age	≥6 Years of Age
Home care	No antibiotics or amoxicillin	Amoxicillin
Inpatient, ward	Ampicillin/amoxicillin	Ampicillin/amoxicillin
Inpatient, ICU or complicated disease ²	Ampicillin or ceftriaxone +/- anti-staphylococcal +/- macrolide	Ampicillin or ceftriaxone +/- anti-staphylococcal +/- macrolide

ICU, intensive care unit ¹Unless specific pathogen identified or known drug allergy ²eg, empyema

prescriptions provided at discharge. For hospitalized patients, this will include therapy received during the first 24 hours of care beginning with ED triage. A patient following treatment according to table 1 will be considered as concordant, whereas deviations from these treatments will be considered discordant.

Secondary outcomes include exclusive use of concordant antibiotic therapy for the entire episode, any use of concordant antibiotic therapy during the first 24 hours of care and for the entire episode, and ED revisits and hospitalizations within 72 hours and 7 days of the index discharge. Index visit is defined as the enrollment ED visit or hospitalization through discharge.

Exploratory outcomes include time to first antibiotic, lack of antibiotics during the first 24 hours of care and for the entire episode, and changes in antibiotics after 72 hours, and death, and for hospitalized children, delayed ICU transfer, defined as >24 hours following hospitalization.

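### SAP Appendix 1, which scores the Phase 1 primary outcome, conflicts with Protocol Table 1 without a stated reason; chiefly, it has no entry for young outpatients managed without antibiotics

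*SAP*

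**What the plan says.** Two current texts define concordance for one outcome.

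- **Protocol 7.2 and Table 1.** The rule is "A patient following treatment according to table 1 will be considered as concordant, whereas deviations from these treatments will be considered discordant". Table 1 lists "No antibiotics or amoxicillin" for home care under 6 years, "Ampicillin/amoxicillin" on the ward, and "Ampicillin or ceftriaxone +/- anti-staphylococcal +/- macrolide" for ICU or complicated disease. Its only stated exceptions are an identified pathogen and a known drug allergy.
- **SAP 4.1, 10.1 and Appendix 1.** SAP 4.1 refers the reader to Appendix 1, and 10.1 says "The antibiotics received by a participant is concordant yes (1) or no (0) based on Appendix 1 table, for this analysis". SO 1 in SAP 10.2 reuses the same analysis for the whole episode.

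The protocol gives the clinical background. Section 1.0 reports that, for outpatients under 6, "the guideline recommended considering withholding antibiotics, recognizing that pneumonia in this population is most often caused by viruses". Section 7.1 says that for young children with mild illness going home "the support tool will offer guidance regarding when a strategy of watchful waiting might be favored over empiric amoxicillin", and that for ward admissions "the tool will advise consideration of oral therapy in children with good oral intake".

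The SAP version table records a clarification of the concordance definitions in version 1.1 (February 2020). It does not list what changed or why.

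**The concern.** The primary outcome is a yes/no score, so the table that assigns the score is the endpoint definition. Protocol and SAP use different tables, and two of the options missing from the SAP's table are forms of care on which the tool itself gives guidance. A provider who follows the tool and withholds antibiotics from a toddler going home, or gives oral amoxicillin on the ward, acts concordantly under the protocol but has no matching entry in the SAP.

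For untreated children the SAP is also silent on the score. Section 10.1 scores the antibiotics received and does not say what happens when there were none. Such children are expected: EO 1 censors them, and EO 2 to EO 4 count them. An analyst could score them 0, leave them out, or fall back on Protocol Table 1 and score them 1. These choices can give different primary results. If the tool increases antibiotic-free care, the first two move the arm difference against the intervention.

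**Working it through.** **1. Size of Appendix 1 in the extracted text.** 24 rows × 5 care columns = 120 cells. 18 are n/a, all outpatient, leaving 102 filled: 6 outpatient, 24 ward and 72 ICU. Eight rows are severe-allergy rows, where Table 1's allergy exception applies, so 16 rows are non-allergic.

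**2. Options in Table 1 that Appendix 1 lacks, counted only where Table 1 would offer them.**

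| Table 1 option | Relevant Appendix 1 cells | Cells listing it |
|---|---|---|
| No antibiotics, home care under 6 | 6 filled outpatient cells; no age column | 0 |
| Ward amoxicillin | 4 cells with no severe allergy, effusion or necrotizing/severe disease (8 if effusion is not counted as complicated) | 0 |
| Macrolide add-on, ICU | 16 non-allergic rows × 3 ICU columns = 48 | 0 |

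**3. Other differences.**
- Plain ampicillin is not listed for any ventilated ICU child; Table 1 allows it.
- Some ICU or complicated cells require an anti-staphylococcal drug (for example, ceftriaxone plus vancomycin with ventilation and shock). Table 1 makes it optional.
- In the other direction, Appendix 1 credits regimens that Table 1 would call discordant. After a prior beta-lactam these are outpatient amoxicillin/clavulanate and ward ceftriaxone. For aspiration they are amoxicillin/clavulanate, ampicillin/sulbactam or clindamycin, if aspiration is not itself complicated disease.

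**4. The plan's own power figure.** SAP 6.2.1 and Protocol 8.1 give 750 per arm, 30% under usual care, alpha 0.05 (taken as two-sided) and a detectable difference of 6.8 points at 80% power. The normal approximation, with p̄ the mean of the two rates, is

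z = [√n·(p2 − p1) − 1.96·√(2p̄(1 − p̄))] / √(p1(1 − p1) + p2(1 − p2))

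With n = 750, p1 = 0.300, p2 = 0.368 and p̄ = 0.334: z = (1.862 − 1.307)/0.665 = 0.834, so power is 79.8%. The stated figure reproduces.

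**5. Illustration of the no-antibiotic gap alone.** The documents give no share of untreated outpatients under 6, so the shares here are assumptions. Let u0 be that share of all usual-care children and u1 = u0 + d the share with the tool. Start from Table 1 rates of 30% and 36.8%, set every other table difference to zero, and ignore clustering.

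- Scored 0: the rates become 30 − u0 and 36.8 − u1, so the difference is 6.8 − d points.
- Excluded: the rates become (30 − u0)/(100 − u0) and (36.8 − u1)/(100 − u1), with n reduced to match. For u0 = 2 and d = 2 this is 28.0/98 = 28.6% v 32.8/96 = 34.2%, with 735 and 720 children.

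With u0 = 2%:

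| Rise d (points) | Scored 0: difference, power | Excluded: difference, power |
|---|---|---|
| 0 | 6.8, 81% | 6.9, 81% |
| 1 | 5.8, 68% | 6.3, 73% |
| 2 | 4.8, 52% | 5.6, 63% |
| 3 | 3.8, 36% | 4.9, 52% |

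Scored 1, as in Table 1, the difference stays at 6.8 points and power at 80%. With d = 2 and scoring 0, taking u0 as 0, 5 or 10% gives power of 51, 55 or 61%. With d = 0, equal losses of 2 to 10% in both arms leave the difference at 6.8 points and power at 81 to 88%. The loss therefore comes wholly from the assumed rise d.

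**The case against.** The best case for the plan is that Appendix 1 is a drug-level elaboration of the protocol's table. SAP 6.1.1 still cites Table 1 for the primary outcome in the protocol's wording, the version log records a clarification, and EO 2 and EO 3 would show any shift to antibiotic-free care. Part of this stands: an analyst might well fall back on the protocol and score an untreated toddler 1. But 10.1 names Appendix 1 alone, the SAP's own Table 1 is its version log, and an exploratory comparison does not repair the primary score.

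A footnote to Appendix 1 may have been lost in conversion from PDF. This stands, and the sponsor can settle it at once. Lost rows are a weaker explanation. Five yes/no factors give 32 combinations, and the eight not listed all combine a prior beta-lactam with severe penicillin allergy. Such rows could not supply the ward amoxicillin entry for non-allergic children.

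A reader might infer three stronger claims that the documents do not support:

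- **That the options are missing from 24 ward cells and 72 ICU cells.** Those totals include severe-allergy cells, and the ward total also includes complicated-disease cells, where Table 1 would not offer the drug. The relevant counts are 4 (or 8) and 48.
- **That the missing macrolide works against the tool.** The tool's macrolide advice in Protocol 7.1 concerns ward admissions, and Table 1's ward row does not list a macrolide either. An uncomplicated ward child given one is outside both tables. No arm-differential effect is shown.
- **That restoring the no-antibiotic, ward amoxicillin and macrolide entries would reconcile the tables.** It would not, because ampicillin for ventilated children, mandatory anti-staphylococcal cover, and the added prior-beta-lactam and aspiration regimens would still differ.

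**Conclusion.** The conflict is real and should be fixed before the primary analysis. As written, the SAP's rule can score as failure, or leave unscored, care that the protocol calls concordant and on which the tool gives guidance. The untreated young outpatient is the main error and ward amoxicillin the second. The macrolide, ICU and added-regimen differences are lesser and need a clinical decision.

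The effect on the result is not known. The documents give no shares of children in the affected cells, and Appendix 1 also credits regimens that Table 1 does not, so neither the net size nor the net direction can be stated. It would be tempting to read the illustration as a forecast of lost power, or as proof of bias against the intervention. It is neither. It depends on an assumed rise in antibiotic-free care, and it takes untreated outpatients out of a 30% rate that the plan draws from a cohort of hospitalized children. It also uses 750 independent children per arm, where the plan itself suggests about 500 effective. It shows only that a differential shift of 1 to 3 points would matter against a 6.8-point target.

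All statements about what Appendix 1 lacks rest on the text extracted from the PDF.

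**What to change.** Before arm-level outcomes are seen:

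1. Add to Appendix 1 that no antibiotics is concordant for home care under 6 years, and that amoxicillin is concordant on the uncomplicated ward. If either omission was intended, say so with the clinical reason and give untreated children an explicit score.
2. State that Appendix 1 so amended governs the primary outcome and SO 1.
3. Have the investigators confirm or restore, with a reason, the macrolide add-on, ampicillin in ventilated children, and the optional status of anti-staphylococcal cover. Then align Protocol Table 1, including the prior-beta-lactam and aspiration regimens.
4. Report the primary outcome scored under Table 1 as it now stands in the protocol as a sensitivity analysis.

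The cost is wording in two documents and a second scoring run. Age, site of care, and medication orders and prescriptions are already collected (Protocol 7.3, SAP 7.1).

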4.0 Study Design and Randomization

4.1 Study Design and Randomization (P1, EHR-based antibiotic decision support)

Effectiveness of the EHR-based antibiotic decision support application for promoting guideline-concordant antibiotic prescribing in children presenting for emergency care will be evaluated in a pragmatic, cluster randomized crossover study conducted over a period of 18 months that includes two respiratory seasons. Our institutions possess demonstrated experience in the execution of these pragmatic designs.¹⁷⁻²¹ Crossover will occur each month in a randomly determined sequence within each hospital. To ensure balanced representation of each arm in periods of both low and high pneumonia prevalence, randomization will occur in 3 permuted blocks (size=6). The cluster-randomized crossover design also improves efficiency and reduces potential problems related to cluster imbalance when using a small number of clusters.⁶⁷ The antibiotic decision support application will be provided to those randomized to the intervention arm, whereas the control arm will receive usual care. Due to the nature of the intervention, blinding of treating providers will not be possible. Importantly, since this is a trial focused on provider behavior, all children will receive standard of care management. All treatment decisions will be made by the clinical providers and will not be restricted or altered in any way.

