8.2 Analysis (P1)

Analyzing data from cluster randomized crossover trials requires accounting for correlations within clusters and time periods. As outlined by Turner et al.,²¹ we will use a hierarchical and mixed effects logistic regression model, a complex analytic approach which offers flexibility regarding model assumptions and incorporation of cluster-level and individual-level covariates. We will also use a weighted, cluster-level logistic regression to compare guideline-concordant antibiotic prescribing between groups. In this analysis, data for each cluster are collapsed into a single summary measure, and the summary measures are then analyzed as if they were raw data, facilitating simple data reporting and interpretation.²¹ Both methods perform well and are used frequently in the analysis for traditional cluster randomized trials without crossover. Important baseline covariates (e.g., age, sex, race, site of care, frequency of bacteremia and other pneumonia-related complications) will also be assessed and included as model covariates. Similar analyses will be conducted for the proposed secondary and exploratory outcomes using hierarchical and mixed effects logistic regression models for binary outcomes and frailty models for time to first antibiotic.

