## **6.3 Randomization**

### **6.3.1 Phase 1**

During the 18-month study period, EHR-based antibiotic decision support will be active monthly (4-week blocks) based on the cluster randomized scheme at each hospital. To ensure balanced representation of each arm in periods of both low and high pneumonia prevalence, randomization will occur in 3 permuted blocks (size=6). The antibiotic decision support application will be provided to those randomized to the intervention arm, whereas the control arm will receive usual care. Participants enrolled during the month with antibiotic decision support will be assigned to the intervention arm, and participants receiving usual care will be in the control arm. Participants will be blinded to the treatment assignments and study staff and providers will not be blinded to treatment arm assignments due to the nature of the interventions.

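### The Phase 1 alpha of 0.05 sits on a site-stratified CMH test that ignores the randomised hospital-months; its type I error is about 11% at the plan's own conservative effective sample size

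*SAP*

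**What the plan says.** **Randomisation.** Protocol 4.1 states: "Crossover will occur each month in a randomly determined sequence within each hospital". It uses three permuted blocks of six. SAP 6.3.1 agrees: "EHR-based antibiotic decision support will be active monthly (4-week blocks) based on the cluster randomized scheme at each hospital". With two hospitals and 18 periods, the randomised units number 36.

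**Alpha.** SAP 7.2 states: "There will be one primary objective per aim evaluated at the alpha 0.05 level". It also says that "analysis of the primary objective will be stratified by site to account for site variation".

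**Analyses.** SAP 10.1 lists three for the Phase 1 primary outcome:

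1. A comparison of the arms "using a Cochran-Mantel-Haenszel method in a stratified analysis by site to control for two sites at the alpha 0.05 level", with a proportion difference and 95% interval.
2. A mixed-effects logistic regression, for which it says: "The month of each participant enrolled will be treated as a random effect".
3. A weighted cluster-level logistic regression on one summary per cluster.

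Only the first has an alpha attached, and no order of priority is given.

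**Protocol.** Protocol 8.2 opens its analysis section with this requirement: "Analyzing data from cluster randomized crossover trials requires accounting for correlations within clusters and time periods". It then names the second and third analyses. It does not mention CMH.

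**Sample size.** Protocol 8.1 and SAP 6.2.1 assume 750 children per arm and 30% concordance under usual care, and state a detectable difference of 6.8 points. Both add that clustering may reduce the effective size, conservatively to about 500 per arm.

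**The concern.** Children seen in one hospital-month share staff, local practice and the circulating pathogens of that month, so their outcomes are likely to be correlated. Stratifying by site removes the difference between the two hospitals. It does nothing about correlation within a hospital-month, which is the level at which treatment was assigned. Followed as written, the Phase 1 claim rests on the one listed analysis that ignores the design, and its p-value and interval are too optimistic.

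The two analyses that could correct this are not only unranked; their key terms are open.

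- **Month** could be a random effect specific to each hospital or one effect shared by both. It could also be the randomised four-week period or a calendar month.
- **Cluster** could be one of the 36 hospital-periods or one of the two hospitals. Protocol 4.1, for example, says that the design "reduces potential problems related to cluster imbalance when using a small number of clusters".

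If CMH is significant and the cluster-aware analyses are not, the SAP does not say which governs.

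**Working it through.** **1. Units.** 2 hospitals × 18 periods = 36 hospital-periods. With 2 × 750 = 1,500 children, the mean size is m = 1500/36 = 41.7.

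**2. The plan's own figure.** With p1 = 0.30, difference d = 0.068, two-sided alpha 0.05, power 80% and pooled variance:

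n = [1.96·√(2·0.334·0.666) + 0.8416·√(0.30·0.70 + 0.368·0.632)]² / 0.068² = 754 per arm.

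Solving for d at 750 per arm gives 6.82 points, so the stated 6.8 reproduces with no allowance for clustering. A one-sided test would give 6.03 points, so two-sided 0.05 is the level the plan used. At 500 per arm the same formula gives 8.4 points, and power for 6.8 points falls to 63%.

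**3. Type I error of CMH.** The implied design effect is DE = 750/500 = 1.5. A test that ignores it has two-sided error 2(1 − Φ(1.96/√DE)):

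2(1 − Φ(1.96/1.225)) = 2(1 − Φ(1.600)) = 10.95%.

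Nominal 95% intervals then cover about 89%. Their width is 1/√1.5 = 0.816 of what it should be, so they are 18% too narrow.

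**4. Range.** No intracluster correlation (ICC) is given, so these values are assumptions. With equal periods, DE = 1 + (m − 1)·ICC.

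| ICC | DE | Type I error of CMH |
|---|---|---|
| 0 | 1.00 | 5.0% |
| 0.005 | 1.20 | 7.4% |
| 0.01 | 1.41 | 9.8% |
| 0.0123 | 1.50 | 10.95% |
| 0.02 | 1.81 | 14.6% |

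**5. Simulation.** Set-up: 36 hospital-periods of 41–42 children, permuted blocks of six within hospital, 30% concordance, no arm effect, DE 1.5, 4,000 trials (Monte Carlo error about ±1 point). The mixed models used likelihood-ratio tests. Weighted least squares on the 36 proportions stood in for the planned cluster-level logistic regression.

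| Analysis | Correlation all within hospital-month | Half of it shared by both hospitals |
|---|---|---|
| CMH by site | 10.8% | 10.9% |
| Mixed model, hospital-period intercept | 5.6% | 5.9% |
| Mixed model, one month effect shared by both hospitals | 9.0% | 7.4% |
| Weighted analysis of 36 proportions | 4.6% | 5.0% |

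A separate simulation of 20,000 trials at ICC 0.0123 gave 10.8% for CMH and 4.8% for the weighted analysis. With an assumed seasonal spread of period sizes these became 12.5% and 6.2%.

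**6. Period length.** 18 four-week blocks last 18 × 28 = 504 days; 18 calendar months last about 18 × 30.44 = 548 days. Calendar months would therefore straddle randomised periods.

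**The case against.** The strongest reply is that no sentence calls CMH the deciding analysis. SAP 7.2 gives alpha to an objective, not to a test. The SAP pairs a simple test with a model for most outcomes, so CMH could be read as the simple comparison. The protocol's requirement and both cluster-aware analyses are on record. This is fair, but it leaves the SAP with alpha wording on CMH alone and no rule that puts another analysis above it.

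Other points have some weight:

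- **Size.** The plan calls 500 per arm conservative, so on its own terms the error lies between 5% and 11%. The 14.6% at ICC 0.02 goes beyond the plan's case.
- **Independence of periods.** The ICC-based figures assume that period effects are independent over time. Blocking in sixes protects against smooth drift. With assumed correlation between adjacent periods of 0.5, 0.8 and 0.9, simulated CMH error at ICC 0.0123 was 9.6%, 7.0% and 6.1%. Inflation shrinks but remains. The 10.95% conditional on a design effect of 1.5 is unaffected.
- **Terms.** SAP 6.3.1 uses month for the randomised block, so the calendar reading is weak. A single summary per hospital could not compare arms, because each hospital receives both, so the two-hospital reading of cluster is strained. Whether the month effect is hospital-specific or shared remains a real question, and step 5 shows that it matters.
- **Calibration of the alternative.** The mixed model with a likelihood-ratio test ran at 5.6% and 5.9%, slightly above nominal. This bears on how the replacement is specified, not on whether CMH should be replaced.
- **Secondary outcomes.** No error rates were computed for these. They carry no alpha adjustment and mixed models are already planned, so that part is less pressing.

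**Conclusion.** The concern holds: SAP 10.1 is wrong as written. The only Phase 1 analysis with an alpha does not respect the unit of randomisation. It does not meet the requirement that the protocol sets, and the protocol does not name it. At the plan's implied design effect of 1.5 its type I error is about 11% (10.95% by formula, 10.8–10.9% by simulation), roughly twice nominal.

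The figure is conditional. It rests on reading 750/500 as the design effect and on a two-sided test. A lower ICC or strong correlation between adjacent periods reduces it; a higher ICC or uneven monthly enrolment raises it. This must be fixed, because it concerns the test of the Phase 1 primary hypothesis.

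**What to change.** In SAP 10.1, name one hospital-period-level analysis as the single alpha 0.05 test. Possible wording: *The Phase 1 test at two-sided alpha 0.05 is the mixed-effects logistic model with fixed effects for arm and site, the prespecified covariates, and a random intercept for hospital × randomised period (36 levels). Month means the randomised period within hospital.* The weighted analysis of 36 summaries would serve equally well as the named test. In either case, state the small-sample reference distribution, because the mixed model ran slightly above 5% in simulation and so did the weighted analysis when period sizes were uneven.

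Also:

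- Define cluster in the weighted analysis as the hospital-period.
- Take the risk-difference interval from a cluster-aware analysis and label CMH as descriptive.
- For SO 1 to SO 5, and for exploratory binary outcomes with enough events, base inference on the mixed models already planned, with the same hospital-period effect. Treat CMH and chi-square results as descriptive.
- For very rare outcomes such as death (EO 5), report counts and percentages by arm.

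The cost is SAP wording, since the analyses are already planned and no new data are needed. The downside is less apparent precision. At a design effect of 1.5, intervals are √1.5 = 1.22 times as wide, and the difference detectable with 80% power rises from 6.8 to 8.4 points.
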